6.3. Management of Non-Malaria Illnesses

Patients who are found to have illnesses other than malaria will receive standard-of-care treatment in the study clinic, according to standardized algorithms, or will be referred to the Tororo District Hospital. We will avoid the routine use of non-study medications with antimalarial activity, including tetracyclines, antifolates (with the exception of assigned chemopreventive regimens), and macrolide antibiotics, when acceptable alternatives are available. In addition, drugs with known risk of torsades de pointes or CYP3A inhibitors (Appendix K and L) will be avoided when prescribing treatment to pregnant women or children during the time they are taking study drugs. If the study clinician deems treatment with one of the drugs listed on Appendix K or L is required, the clinical management team will be consulted. During follow-up for non-malarial illnesses, blood smears will be done at the discretion of the study physician if the subjects are febrile (tympanic temperature $\geq 38.0^{\circ}\text{C}$) or report history of fever in the past 24 hours. If the blood smear is positive, the patient will be diagnosed with a new episode of malaria and managed per study protocol.

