[figure not shown]
Figure 1. Prevalence of key antifolate resistance-conferring mutations over time

Clinical trials of DP. DP is a new co-formulated ACT that was approved for use in Uganda in 2005. We have completed two standard clinical trials in Uganda comparing DP to AL,^{50, 74}. These trials were conducted at sites with both low (Kanungu) and high (Apac) malaria transmission intensity, enrolling 835 patients, including 741 children under the age of 5 years. Both drugs were highly efficacious, with a low risk of recrudescence after therapy. Relevant to this proposal is the drugs' post-treatment prophylactic effect up to one month after therapy. One month after therapy, risks of recurrent parasitemia with DP were 4% and 11% at the low and high transmission sites, respectively, compared to risks of 18% and 29% with AL ($p < 0.0001$ for both comparisons). In addition, DP was better tolerated than AL at both sites, with no serious adverse events related to DP.

More recently we completed a longitudinal clinical trial comparing DP to AL in a cohort of young children in Tororo (manuscript submitted for publication). Overall, 312 children were randomized to DP or AL at the time of the first episode of uncomplicated malaria (median age 10.5 months). The same treatment was given for all subsequent episodes of uncomplicated malaria and children were followed until they reached 5 years of age. The cohort included a subgroup that was HIV-infected or HIV-exposed prescribed TS prophylaxis. Outcomes included time to recurrent malaria following individual treatments and the overall incidences of treatments for malaria, complicated malaria, and hospitalizations. Among children not prescribed TS prophylaxis, 4443 treatments for malaria were given over 790 person years following randomization. Treatment with DP was associated with a less than 5% risk of recurrent malaria within 28 days and a lower hazard of recurrent malaria over 84 days compared to AL (HR=0.66, 95% CI 0.61-0.70, $P < 0.001$)(Figure 2). Children randomized to DP also had a lower incidence of all treatments for malaria (IRR=0.85, 95% CI 0.75-0.96, $P = 0.01$), complicated malaria (IRR=0.12, 95% CI 0.04-0.39, $P < 0.001$), and hospitalizations (IRR=0.31, 95% CI 0.13-0.77, $P = 0.01$). In addition, repeated treatments with DP were safe, with a low risk of adverse events that were comparable to AL.⁷⁵

Figure 2. Cumulative risk of recurrent malaria following treatment with DP vs. AL

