1.3. Rationale

Malaria remains one of the most important infectious diseases worldwide with an estimated 3.3 billion people at risk leading to hundreds of millions of cases and 660,000 deaths each year.^{46, 76} In 2010, 81% of cases and 91% of deaths were estimated to have occurred in Africa, with children under five years of age and pregnant women most severely affected.⁴⁶ The primary tools currently available for malaria prevention in Africa include ITNs and IPTp. However, there are limitations with these interventions and the burden of malaria remains high in many parts of Africa despite recent increases in coverage levels. ITNs do not fully protect against malaria and there is concern for waning efficacy given the emergence of resistance to pyrethroid insecticides (the only class used in ITNs).^{32, 33} The only drug widely used for IPTp is SP, and there are recent reports suggesting that IPTp with SP is no longer effective, especially in East Africa, where resistance to this drug is now widespread.^{14, 77} Recent increases in funding for malaria control offer an unprecedented opportunity to expand preventative interventions; however, new strategies are urgently needed to reduce the burden of malaria for those at greatest risk.

One of the most important malaria control interventions is the use of ACTs for the treatment of malaria. ACTs are highly efficacious, and now the recommended first-line treatment for uncomplicated falciparum malaria in all countries of sub-Saharan Africa, including the treatment of malaria in pregnant women during the 2nd and 3rd trimesters.²⁵ ACTs also offer the opportunity to greatly reduce the burden of malaria in pregnant women and young children if their role is expanded to chemoprevention. IPT with the ACTs artesunate-amodiaquine, artesunate-SP, and DP have been shown to be effective and safe for the prevention of malaria in African children.^{41, 78, 79} IPT with DP is especially attractive given its

prolonged post-treatment prophylactic effect, due to the unusually long half-life of piperazine.²⁷

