6.12. Management of Adverse Events Potentially Related to Study Drugs

The following section outlines management of adverse events potentially related to study drugs (SP or DP). Given the double blinded nature of the intervention, study clinicians and study participants will not be aware of what study drugs are being administered. Therefore all study participants will be considered potentially exposed to either study drug during the period study drugs are first given up to one month after the last dose of study drug is given.

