7.1.2. Identification of Adverse Events

At each scheduled and unscheduled visit to the clinic, study clinicians will assess patients according to a standardized case record form. A severity grading scale, based on toxicity grading scales developed by the NIH Divisions of AIDS (DAIDS) and the Division of Microbiology and Infectious Diseases (DMID) Pediatric Toxicity Tables, will be used to grade severity of all symptoms, physical exam findings, and laboratory results (Appendix J). All participants, regardless of treatment arm, will be assessed using the same standardized case record form. Adverse event monitoring will occur during the period when study drugs are given and up to 1 month after cessation of study drugs.

Data will be captured on the incidence of all adverse events, regardless of severity. For each adverse event identified and graded as severe or life threatening and felt to be possibly, probably or definitely related to study drugs, an adverse event report form will be completed. In addition, an adverse event form will be completed for all serious adverse events and unexpected events, regardless of severity. An adverse event report form will not be completed for events classified as mild or moderate (unless they are serious or unexpected), as mild and moderate symptoms are common and difficult to distinguish from signs and symptoms due to malaria and other common illnesses. The following information will be recorded for all adverse experiences that are reported:

- 1) Description of event
- 2) Date of event onset
- 3) Date event reported
- 4) Maximum severity of the event
- 5) Maximum suspected relationship of the event to study drugs (either SP or DP)

- 6) Whether the event is a serious adverse event
- 7) Initials of the person reporting the event
- 8) Outcome
- 9) Date event resolved

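### Section 6.3 ends the avoidance of torsades-risk drugs and CYP3A inhibitors with dosing, although the protocol treats participants as potentially exposed for one further month

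*Protocol*

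**What the plan says.** Section 6.3 contains three rules that bear on this point.

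- **Avoidance of Appendix K and L drugs.** Torsades-risk drugs and CYP3A inhibitors "will be avoided when prescribing treatment to pregnant women or children during the time they are taking study drugs". This rule has a time limit.
- **Consultation.** The next sentence begins "If the study clinician deems treatment with one of the drugs listed on Appendix K or L is required" and requires that the clinical management team be consulted. It has no time limit of its own.
- **Drugs active against malaria.** "We will avoid the routine use of non-study medications with antimalarial activity", with macrolides among the named classes, when acceptable alternatives exist. This rule also has no time limit, but it covers routine use only.

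Elsewhere the protocol describes exposure that outlasts dosing. Section 6.12 regards every participant as potentially exposed "during the period study drugs are first given up to one month after the last dose of study drug is given". Section 7.1.2 states: "Adverse event monitoring will occur during the period when study drugs are given and up to 1 month after cessation of study drugs". Section 1.3 explains DP's prolonged effect as "due to the unusually long half-life of piperazine" (read here as piperaquine, DP's partner drug). Section 1.2 describes a "post-treatment prophylactic effect up to one month after therapy" and, in a later cohort, "a lower hazard of recurrent malaria over 84 days compared to AL".

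**The concern.** The avoidance rule exists because of drug exposure, not because of the act of dosing. Appendix L, by its title, lists drugs that may inhibit the partner drug's metabolism, so the list matters for as long as that drug is present. The protocol's own convention is that exposure may last a month beyond the final dose. It watches for adverse events through that month, but the prescribing precaution stops when dosing stops.

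The study clinic is still the main prescriber at that time. Women are followed to about 6 weeks postpartum and children to 36 months of age, and both are told to use the clinic for all medical care. At stake is a listed drug being given soon after an active DP course, with no stated duty to avoid it and an unclear duty to consult.

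**Working it through.** The plan gives no figure to reproduce. The check compares the time windows and then counts who can fall between them.

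**1. Windows side by side**

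| Rule | Starts | Ends |
|---|---|---|
| 6.3 avoidance of Appendix K and L drugs | while taking study drugs | end of dosing |
| 6.3 consultation | not stated | not stated |
| 6.12 potential exposure | first dose | last dose + 1 month |
| 7.1.2 adverse-event monitoring | dosing period | last dose + 1 month |

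I read the 6.3 window generously, as the whole dosing period including the intervals between courses. On that reading the uncovered time is one month after the last dose. No other section extends the avoidance rule.

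**2. Children.** Section 5.4 allows dosing to 104 weeks of age, and Appendix D gives active DP at week 104 in both infancy schedules. Every child who completes dosing therefore enters the uncovered month directly after active drug. The number expected to reach 24 months is 81 + 4 × 41 = 245 from Table 9, or 162 + 81 = 243 from Table 10.

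**3. Women.** Assigned to DP: 100 + 100 = 200. Expected to have placental outcomes: 90 + 90 = 180 (Table 9). Take one month as 4 weeks. For delivery at week D and last active course at week L, the weeks of potential exposure left after delivery are R = max(0, 4 − (D − L)). Course weeks come from Appendix D: 16, 20, 24, 28, 32, 36 and 40 for monthly DP; 20, 28 and 36 for 3-dose DP.

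| Delivery week D | Monthly DP, R | 3-dose DP, R |
|---|---|---|
| 28 | 4 if that course was given, else 0 | 4 if that course was given, else 0 |
| 29, 30, 31 | 3, 2, 1 | 3, 2, 1 |
| 32 | 4 if that course was given, else 0 | 0 |
| 33, 34, 35 | 3, 2, 1 | 0, 0, 0 |
| 36 | 4 if that course was given, else 0 | 4 if that course was given, else 0 |
| 37, 38, 39 | 3, 2, 1 | 3, 2, 1 |
| 40 | 4 if that course was given, else 0 | 0 |
| 41, 42 | 3, 2 | 0, 0 |

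For example, delivery at week 38 gives 4 − (38 − 36) = 2 weeks in either DP arm. All these intervals lie inside the 6-week postpartum follow-up.

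**4. Permanent discontinuation.** Under 6.14, study drugs are normally held once a grade 3 or 4 event is confirmed. They are stopped for good if a possibly related event lasts more than 28 days or recurs on re-challenge. On the first route the last dose is already about 28 days old, so little of the extra month remains. Mainly the re-challenge route leaves someone recently dosed.

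**5. Drugs left to the time-limited rule.** Appendix K lists 42 and Appendix L lists 8, with 2 on both: 42 + 8 − 2 = 48. The untimed rule on antimalarial activity reaches 5 of them (azithromycin, clarithromycin, erythromycin, chloroquine, halofantrine): 48 − 5 = 43. Nine of those are marked off the US or world market: 43 − 9 = 34, including 6 of the 8 in Appendix L. This shows that the untimed rule does not close the gap. It does not measure risk.

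**The case against.** The strongest case against is that ending a precautionary co-medication rule when dosing ends is a legitimate design choice, and that nothing in the protocol shows a hazard afterwards. Much of this stands.

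- **Evidence of persistence.** The one-month and 84-day findings in 1.2 concern recurrent parasitaemia and malaria, not QT effect. Section 1.3 gives no half-life figure. The only QTc data (10.2.3: 145 ECGs in 19 children on DP) were within normal limits, though they are few and not reported as a test of co-medication.
- **Consultation.** A reader might infer that the consultation step lapses after the last dose. The text does not say so. The sentence has no time limit, and taken literally it continues. That it lapses could only be inferred from its place as the exception to a time-limited rule. What can be said is that its scope is unclear.
- **Contradiction.** A reader might also see a conflict with 6.12 and 7.1.2. There is none: those sections govern adverse events, not prescribing, and they cover SP as well as DP.
- **Size of the groups.** Women on 3-dose DP who deliver at weeks 32 to 35 or 40 to 42 have no residual exposure by the protocol's convention. The SP arm receives no DP in pregnancy. Participants taken off study drug are a small residual group.
- **Length of the lists.** They include anti-cancer drugs, antiarrhythmics and a general anaesthetic, so a count of names says little about likely prescribing.
- **Hospital wards.** After-hours prescribing at the hospital's discretion (6.4) applies equally during dosing and does not follow from the post-dose window.

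These points limit the weight of the concern. They do not supply the missing end date: the avoidance rule still stops a month before the protocol's own exposure period does.

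**Conclusion.** The point holds as a minor participant-safety improvement. The Appendix K and L avoidance rule has no post-dose period, and the reach of the consultation sentence after dosing is unclear. Those mainly affected are children after the week-104 course and women who deliver within about 4 weeks of an active DP course.

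The size of the risk cannot be computed. The protocol gives no prescribing frequency for the listed drugs, no half-life figure and no post-dose QT effect. It does not support a claim of demonstrated harm, and no endpoint or analysis is affected.

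The conclusion assumes that the time of taking study drugs means the dosing period including intervals between courses, and that one month is 4 weeks (31 days would add about 0.4 week). One month is the protocol's exposure convention, not a derived washout.

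**What to change.** In 6.3, state that both the Appendix K and L avoidance and the consultation step apply from the first dose of study drug until at least one month after the last dose. State that this holds in all arms, because clinicians are blinded, and that it includes postpartum women. Defined by the last dose, the window also covers anyone permanently taken off study drug, so no separate rule is needed.

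The cost is one sentence, slightly fewer drug options and a few more consultations for one month. Listed drugs could still be used after consultation when required.

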6.2. Diagnosis and Management of Malaria

Patients found to have malaria based on laboratory confirmation will have a second finger prick for a thin smear (to determine parasite species), hemoglobin measurement using a portable spectrophotometer (HemoCue), and collection of plasma for future PK studies. All episodes of malaria will be classified as uncomplicated or complicated based on the following criteria:

Uncomplicated malaria (all of the following)

- 1) Fever ($\geq 38.0^{\circ}\text{C}$ tympanic) or history of fever in the previous 24 hours
- 2) Positive thick blood smear
- 3) Absence of complicated malaria

Complicated malaria (any of the following)

- 1) Evidence of severe malaria (Appendix F) and parasitemia
- 2) Danger signs present in children (Appendix F) and parasitemia

Episodes of malaria will also be classified into the following categories according to the timing of previous malaria episodes for treatment purposes:

1. New episodes of malaria will be defined as any first episode or any episode occurring > 14 days after the diagnosis of a previous episode
2. Treatment failures will be defined as any of the following:
 - a. Complicated malaria occurring 1-14 days after the diagnosis of a previous episode
 - b. Fever ($\geq 38.0^{\circ}\text{C}$ tympanic) or history of fever in the previous 24 hours with a parasite density \geq the parasite density of an episode of malaria diagnosed 2 days prior

- c. Fever ($\geq 38.0^{\circ}\text{C}$ tympanic) or history of fever in the previous 24 hours with a parasite density $\geq 25\%$ of the parasite density of an episode of malaria diagnosed 3 days prior
- d. Fever ($\geq 38.0^{\circ}\text{C}$ tympanic) or history of fever in the previous 24 hours with a positive thick blood smear of any parasite density occurring 4-14 days after the diagnosis of a previous episode

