All patients diagnosed with new episodes of uncomplicated malaria will be prescribed AL, the recommended first-line treatment in Uganda for children and pregnant women in their 2nd or 3rd trimester. Patients with complicated malaria will be prescribed quinine or artesunate according to national malaria treatment guidelines. Children who are less than 4 months of age or weigh $<5\text{kg}$, will be treated with quinine for uncomplicated malaria in accordance with the Uganda Ministry of Health Guidelines. Patients with treatment failure within 14 days following treatment with AL will be prescribed quinine according to national malaria treatment guidelines. Patients with treatment failure within 14 days following treatment with quinine or artesunate will be treated with quinine plus clindamycin or artesunate.

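### Section 6.3 labels any positive smear during follow-up of a non-malarial illness a new episode, without the 14-day condition in section 6.2, so read literally it can point to AL where 6.2 requires quinine

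*Protocol*

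**What the plan says.** Section 6.2 sorts malaria episodes by timing and says what the sorting is for: "Episodes of malaria will also be classified into the following categories according to the timing of previous malaria episodes for treatment purposes".

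- **New episode.** "New episodes of malaria will be defined as any first episode or any episode occurring" more than 14 days after a previous diagnosis.
- **Treatment failure, item 2d.** Current or recently reported fever together with this smear result: "positive thick blood smear of any parasite density occurring 4-14 days after the diagnosis of a previous episode".

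The same section then ties the drug to the category:

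- "All patients diagnosed with new episodes of uncomplicated malaria will be prescribed AL".
- "Patients with treatment failure within 14 days following treatment with AL will be prescribed quinine".
- Children under 4 months or under 5 kg get quinine for uncomplicated malaria.
- "Patients with complicated malaria will be prescribed quinine or artesunate according to national malaria treatment guidelines".

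Section 6.3 covers patients being followed for an illness other than malaria. There, "blood smears will be done at the discretion of the study physician if the subjects are febrile" or report recent fever. If the smear is positive, "the patient will be diagnosed with a new episode of malaria and managed per study protocol".

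Sections 4.4 and 6.5 deal with febrile, smear-positive patients at enrolment and at routine visits. Both diagnose malaria and refer to section 6.2 for treatment. Neither assigns a timing category.

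**The concern.** *New episode* is a defined term in section 6.2, with a day limit, and it selects the drug. Section 6.3 applies the term to every positive smear in its setting and leaves the day limit out. A patient treated with AL a week earlier, who is now febrile and smear-positive, is a treatment failure by the 6.2 definition and a new episode by the 6.3 sentence.

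What is at stake is patient care: a clinician who takes 6.3 at its word would repeat AL where 6.2 calls for quinine.

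**Working it through.** There is no figure in the plan to reproduce. The check sets the two sections side by side and follows one patient through them.

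**Length of the overlap**

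- In 6.2, *new* requires more than 14 days since the previous diagnosis, so it starts on day 15. The unconditional 6.3 label disagrees with that definition on days 1 to 14.
- Item 2d runs from day 4 to day 14 inclusive: 14 − 4 + 1 = 11 days. It needs only fever and a positive smear of any density. The 6.3 smear is taken because the patient is febrile or reports fever, so a positive result in this window always meets 2d.
- Items 2b and 2c add days 2 and 3, but only when parasite density reaches a set level. They are not counted here.

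**A patient who gets there by following the protocol**

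| Day | Finding | Section that applies | Result |
|---|---|---|---|
| 0 | Uncomplicated malaria | 6.2 | New episode, AL |
| 5 | Fever, smear negative | 6.1, which hands over to 6.3 | Managed as a non-malarial illness |
| 8 | Fever, smear positive | 6.3, read literally | New episode, hence AL |
| 8 | Same finding | 6.2 item 2d | Treatment failure, hence quinine |

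**Where the drug conflict does not arise**

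- Complicated malaria: the options are quinine or artesunate, so AL is not in question.
- Uncomplicated malaria in children under 4 months or under 5 kg: a new episode already gets quinine.
- More than 14 days after the previous diagnosis, or with no previous episode: both sections say *new*.
- Routine visits: section 6.5 refers straight to 6.2.

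**Effect on the outcomes**

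Sections 8.2.1 and 8.3.1 count a treatment for malaria as an incident case only if no other treatment was given in the previous 14 days. In the example, the day 8 treatment follows the day 0 treatment by 8 days. It is not counted, whichever label or drug is used.

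**The case against.** The strongest reply is that 6.2 already settles the matter. Its timing categories are general, carry explicit day counts, and make no exception for malaria found during another illness. The 6.3 sentence ends by sending the patient to management under the protocol, and in clinic that means section 6.2. In context, *new episode* may mean only that the illness is now malarial rather than non-malarial. Most of this stands, and a sensible clinician would probably apply 6.2 and give quinine. What it does not remove is the order of the sentence: 6.3 assigns one of the 6.2 categories first and refers to management second, so a literal reader reaches the treatment rules already holding the label that leads to AL.

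The reply also says that the sequence is narrow. That stands too. A febrile patient who enters 6.3 from 6.1 needs an AL-treated episode, then a smear-negative fever, then a smear-positive fever, with the last falling on days 4 to 14. The documents do not say how often this happens.

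A reader might infer two stronger points, which the documents do not support:

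- *The label distorts the incidence of malaria or favours an arm.* The incident-case rule depends on the dates of treatments and not on the label, and nothing in the text makes the labelling differ by arm.
- *Section 6.1 requires a smear at every febrile visit, so the discretion in 6.3 contradicts it.* Section 6.3 limits that discretion to follow-up of non-malarial illnesses, and 6.1 hands smear-negative patients to 6.3. That is a specific rule following a general one. How far the discretion should extend is a matter of detail or preference, not an error.

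**Conclusion.** The point holds as a minor wording error in a treatment instruction. Section 6.3 uses a term defined in 6.2 without its condition. In the 11-day window after an AL-treated episode, its label contradicts item 2d and, read literally, leads to AL instead of quinine. This concerns uncomplicated malaria in patients who are not under 4 months or under 5 kg.

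The risk is small, because the reference to protocol management probably brings clinicians back to 6.2. That is a judgement about how the sentence will be read; the text does not guarantee it. No frequency is claimed. The point deserves correction for patient care, since the literal route repeats the drug that 6.2 says to change. It has no consequence for the incidence analyses or the comparison between arms.

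**What to change.** In section 6.3, change the end of the sentence on a positive smear so that the patient is diagnosed with *malaria, classified and treated as in section 6.2*. This removes the timing label and makes the referral explicit, as sections 4.4 and 6.5 already do.

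The cost is one phrase. No visit, test, drug, outcome definition or analysis changes, and the smear rules in 6.1 and 6.3 can stay as they are.
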